**Research question(s):**

1. Primary goal is to study the effect of the surgical technique (flap elevation or flapless) on the change in soft tissue (papillary height and facial margin level) between pre-operative level and up to 12-18 months following immediate implant placement and crown temporization.
2. Second goal is to study the effects of surgical technique (flap or flapless) and horizontal/vertical extraction socket dimensions on the lateral ridge dimensions and interproximal bone level adjacent to the implant 12-18 months following surgery.

**Scientific abstract:**

Immediate implant placement following tooth extraction has become a predictable method of therapy. Advantage of this method combined with immediate temporization, is evident in the maxillary esthetic zone, since it allows most continuous support of soft tissue contour. Surgical implant placement can be accomplished following elevation of a soft tissue flap or with a flapless approach. Numerous studies have demonstrated alveolar ridge remodeling with net bone loss at 6 months following elevation of flap (Schropp and Isidor, 2008, Buser et al., 2011). It is not clear, how this finding affects clinical changes in ridge dimensions (soft and hard tissue). Several uncontrolled trials have reported outcomes using the flapless technique (Raes et al., 2011, Van de Velde et al., 2010, Block et al., 2009), but no randomized controlled studies comparing these two methods are available. The aim of this study is to compare 1) the remodeling of the gingival tissue margin (change in papillary distance, gingival margin level / recession), and 2) the dimensional changes of the ridge and the stability of the radiographic alveolar bone level following immediate implant placement, temporization and restoration with or without flap elevation.

**Lay abstract:**

In implant dentistry, immediate implant placement is a reliable and predictable treatment. For patients who need implant therapy in the anterior region of the mouth, length of therapy and esthetic outcomes are of primary concern. Currently, one of the two surgical techniques are utilized for implant placement: flap elevation method or flapless method. However, there are no prospective longitudinal studies comparing the advantages and disadvantages of these two techniques on soft and hard tissue stability in the area. The aim of this study is to compare biological (soft and hard tissue remodeling) and esthetic outcomes of the two techniques.

**Study Purpose and Rationale:**

Introduction of the immediate implant concept is attributed to Schulte (1976). The earliest clinical case reports were published about 20 years ago (Lazzara, 1989, Ross et al., 1989). Today immediate implant placement has been established as a reliable and predictable therapy, with similar survival and success rates to delayed implantation (Schropp et al., 2003, Block et al., 2009). Survival rates for both procedures included in a recent systematic review exceeded

95% (Chen et al; 2009). Comparison of histological healing has demonstrated no significant difference in bone to implant contact in immediate and delayed implant placement (Paolantonio et al., 2001). Teeth scheduled for extraction and immediate implantation, as a result of extensive caries, endodontic failures, root perforations and fractures, often present with radiographic evidence of previous infections, in form of periapical radiolucency. No significant differences have been shown between implants placed in healthy versus previously infected extraction sockets, in terms of success and survival rates (Novaes and Novaes, 1995, Villa and Rangert, 2005, Lindeboom et al., 2006, Siegenthaler et al., 2007, Crespi et al., 2010, Waasdorp et al., 2010) and histological results (Novaes et al., 1998, Novaes et al., 2003, Shabahang et al., 2003, Chang et al., 2009), as long as the site is thoroughly debrided following removal of the tooth, primary implant stability is achieved, and in most cases, some type of antibiotic coverage is introduced.

Intentional palatal orientation of immediate implants in maxillary anterior extraction socket or central to palatal orientation of immediate implant in bicuspid extraction socket usually results in a residual horizontal gap between the implant shoulder and the buccal aspect of the socket. This horizontal gap is referred to as Horizontal Defect Dimension (HDD). Width of HDD is dependent not only on the diameter of the extracted root at a given level and the position of the osteotomy, but also on the diameter of the selected implant to replace the tooth. The significance of the width of HDD on the healing has been addressed in numerous studies, with earlier studies suggesting threshold of 1.5mm or less (Akimoto et al., 1999, Wilson et al., 1998) for optimal bone to implant contact and, possibly, beneficial effect on osseointegration. Regenerative materials, bone grafts and barrier membranes, have been used in the past to address the gap between implant and bone at the time of immediate implantation, even in cases of intact buccal and interproximal bone levels, with rationale of epithelial exclusion from the

healing site, preservation of the ridge dimensions and maintenance of soft tissue stability (Chen et al., 2007, Araujo et al., 2011). However, a number of studies demonstrated successful immediate implant outcomes without use of grafting materials (Paolantonio et al., 2001, Covani et al., 2004, Sanz et al., 2010), including histological evaluation and confirmation of predictable new bone formation in HDD of up to 2 mm (Paolantonio et al., 2001). In addition, wider HDD (up to 3 mm) healing with new bone, following extraction and immediate implant placement has also been demonstrated in clinical studies (Schropp et al., 2003; (Botticelli et al., 2004). Favorable peri-implant soft tissue healing, including post-operative midfacial gingival margin and papillary height at 12 months, as well as high patient satisfaction were reported in a prospective study evaluating immediate implant placement and temporization, without utilization of grafts or barrier membranes (Kan et al., 2003).

Immediate implant placement does not preclude vertical and horizontal alveolar ridge loss following the extraction. In a study of hard tissue changes following immediate implant placement in 21 human extraction sites, significant postsurgical dimensional alterations were noted at 4 months following implant surgery (horizontal resorption amounting to 56% of the buccal bone and 30 % of the lingual bone), in spite of predictable new bone formation at the inner side of the extraction socket (Botticelli et al., 2004). Mucoperiosteal flaps were elevated in this study prior to extraction and implant placement. Elevation of full thickness flap induces accelerated bone remodeling of alveolar bone and net bone loss in the range of 0.5-1.0mm between 3 and 6 months following surgery (Donnenfeld et al., 1964, Wood et al., 1972, Pennel et al., 1967, Moghaddas and Stahl, 1980, Gomez-Roman, 2001). The question then arises, whether flapless immediate implantation will result in diminished horizontal bone loss, entailing enhanced ridge stability during the first 6 months following surgery. Therefore, the second aim of our study is to investigate the impact of surgical technique and extraction socket dimensions on the changes of the lateral ridge dimension and the interproximal bone level adjacent to the implant up to 12-18 months following surgery.

### **Summary of Study Purpose**

1. To study the effects of the surgical technique on the soft tissue changes following extraction and immediate implant placement and temporization over a 12-18-month period.
2. To study the effects of the surgical technique and the horizontal/vertical defect dimension on the dimensional changes of the lateral ridge and the interproximal bone over a 12-18-month period.

### **Study Design and Statistical Procedures Overview**

We propose to conduct a randomized controlled trial with two treatment arms: one in which immediate implant placement after tooth extraction is carried out after conventional mucoperiosteal flap elevation, and another that will adopt a flapless approach. Only maxillary teeth in the esthetic zone will be included. The primary outcome of the study is the gingival margin alterations at 12-18 months after surgery while the secondary outcome is the dimensional changes of the ridge at 12-18 months.

### **Power Calculations and Statistical Analysis**

Based on similar data published in the literature, we have calculated that 17 subjects per group need to be recruited in order to have 80% power to detect a 0.5mm difference in soft tissue

changes between the two experimental groups. We plan to enroll a total of 40 subjects to account for potential dropout. Differences in the primary and secondary outcomes (changes in soft tissue, ridge dimension and bone level) overtime within each group will be examined as follows: continuous measurements will be summarized using mean/SD or median (interquartile range) for non-normal data. Differences between the two groups will be assessed using two sided t-test (means) or Wilcoxon Rank-Sum test (medians). Categorical measurements will be summarized using proportions. Differences between the two groups will be assessed using chi-square test or Fisher's Exact test for small counts.

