### **Study Procedures**

After informed consent is obtained, and initial periodontal therapy, whenever indicated, the scheduled extraction will be carried out without flap elevation, and the socket will be debrided meticulously. After verification that the local anatomical inclusion criteria are met, patients will be randomized to one of two treatment groups, a test (flapless group) and a control group (flap group). In the test group, the implant will be placed according to standard protocol at a position engaging the palatal wall without elevation of a mucoperiosteal flap. In the control group, intrasulcular incisions will be carried out from one tooth distal to one tooth mesial to the extraction site and full thickness flaps will be elevated with periosteal elevator, including the papillae. The implant will be placed according to standard protocol at a position engaging the palatal wall, and the flaps will be sutured using a combination of interrupted and mattress sutures.

In both groups, temporary restorations will be delivered immediately after implant placement provided that the implant shows primary stability and has engaged in the bone with an insertion torque of 25Ncm or more (Norton, 2004). In case of a lower insertion torque, the protocol will be abandoned, a cover screw will be placed, and a two stage implant protocol will be followed. All patients will be advised to receive a permanent restoration 6 months after surgery, if the implant is deemed to be successful (Misch et al., 2008).

All patients will receive antibiotics 1 hour prior to surgery (Amoxicillin 1g; in allergic patients Clindamycin 300mg) and will continue with Amoxicillin 500mg (Clindamycin 150 mg) tid for seven days following surgery. All patients will be seen 1 week following surgery (suture removal visit, if applicable), review of OH; at two weeks following surgery, follow up of healing and OH; at 4 weeks, 6 weeks and 8 weeks (prophylaxis and measurements); at 3 months (prophylaxis and measurements); at 6 months (prophylaxis, measurements; removal of temporary restorations and impressions for permanent prosthesis, which will be delivered subsequently, can be done by restorative dentist or student at this visit or later) and at 12-18 months (prophylaxis, measurements).

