### **Research Procedures**

A reference notch will be made on the temporary crown with #1/2 bur at a 2 mm distance from the gingival margin at the mesiobuccal, midbuccal and distobuccal sites. The following measurements will be carried out:

1)Soft tissue distance from each of the three notches (mesiobuccally, midbuccally and distobuccally, respectively) at implant placement visit, following suturing, 4weeks, 6 weeks, 8 weeks, 3 months and 6 months. At 12-18 months these measurements will be performed using acrylic stent recoding previous reference points.

2a) Horizontal defect dimension (HDD) defined as horizontal distance from the implant shoulder to the alveolar socket wall, measured in 3 sites: mesial, buccal and distal; measured only at implant placement visit.

2b) Vertical defect dimension (VDD) defined as vertical distance from implant shoulder to the apical contact with the socket wall, measured in 3 sites: mesial, buccal and distal; measured only at implant placement visit.

2c) Buccal soft tissue and buccal plate thickness will be measured following the extraction using digital calipers (one measurement/ midbuccal/6mm apical to gingival margin); measured at implant placement only.

2d) Pocket depth (PD): pocket depth is defined as the distance from the gingival margin to the tip point of the probe (Williams probe). PDs will be measured at 6 sites per tooth, (mesiobuccal, midbuccal, distobuccal, distopalatal, midpalatal, mesiopalatal); measured before surgery and at 6months and 12-18 months.

2e) Buccal dimension of the ridge at the site of implant placement: measured after implant placement during surgery, at 3 months, 6 months and at 12-18 months.

2f) Impressions for study models will be taken first visit, following implant placement and temporization (on the day of surgery), at 8 weeks, 6 months and 12-18 months.

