### **Inclusion Criteria**

- Age 18 or older
- Systemically healthy patients or patients with controlled common systemic conditions (controlled hypertension, controlled diabetes HbA1c up to 7.5 %).
- Presence of both adjacent teeth
- Esthetically acceptable buccal gingival margin position prior to surgery, compared to neighboring teeth and contralateral tooth.
- Radiographic bone level distance from CEJ interproximally up to 5 mm.
- Location of buccal alveolar crest within 4 mm from the free gingival margin, verified after the extraction, before randomization; and fenestration, if present, up to 5mm in diameter at the apical part of the root and affecting less than 50% of the buccal socket wall.

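### Optional gain: the midbuccal margin change could be adjusted for the buccal thickness already collected, once that reading is defined and fixed before randomisation

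*Combined protocol and SAP*

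**What the plan says.** Power Calculations and Statistical Analysis covers continuous outcomes with one sentence: "Differences between the two groups will be assessed using two sided t-test (means) or Wilcoxon Rank-Sum test (medians"). Categorical measurements get chi-square or Fisher's exact tests. No covariate, regression model or stratification factor appears anywhere in the document.

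Research Procedures item 2c reads "Buccal soft tissue and buccal plate thickness will be measured following the extraction using digital calipers", with the details "one measurement/ midbuccal/6mm apical to gingival margin" and "measured at implant placement only". Item 1 of the same section defines the soft-tissue measurement as "Soft tissue distance from each of the three notches (mesiobuccally, midbuccally and distobuccally, respectively"), and the first research question concerns "the change in soft tissue (papillary height and facial margin level").

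On sequence, Study Procedures places extraction first and then says "After verification that the local anatomical inclusion criteria are met, patients will be randomized to one of two treatment groups"; flap elevation (control arm) and implant placement follow. Inclusion Criteria requires "Location of buccal alveolar crest within 4 mm from the free gingival margin, verified after the extraction, before randomization".

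Study Purpose and Rationale cites a systematic review that lists thin biotype and a thin or damaged facial wall among the risk indicators for recession after immediate placement.

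**The concern.** The protocol's own rationale treats tissue and wall thickness as prognostic for recession, and the protocol collects a thickness reading on every patient, but the stated analysis leaves it unused. In a trial of 34 to 40 patients, a prognostic baseline covariate can narrow the interval for the treatment difference without more patients or visits. It also allows for a chance imbalance in thickness between two small arms.

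The reading cannot yet serve as a baseline covariate, for two reasons. Its timing is given both as after the extraction and as at implant placement, and randomisation falls between those two events. Its content is given as one measurement although two tissues are named. If it were taken after allocation or after a flap had been raised, adjusting for it could introduce bias.

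**Working it through.** **Inputs.** From the analysis section: difference 0.5 mm, 17 per group, 80% power, two-sided t-test, 40 enrolled. From Study Purpose and Rationale: SD of midbuccal change 0.53 mm, in a prospective case series of 35 immediate implants. Not in the documents and therefore assumed: alpha 0.05, the SD behind the sample size, R² between thickness and outcome, and a normally distributed covariate.

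**The plan's own figure.** Unadjusted power comes from the noncentral t with 2n − 2 df and noncentrality 0.5 / (SD × √(2/n)).

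- SD 0.50, n = 17: 0.5 / (0.50 × √(2/17)) = 2.92; power 80.7%. The stated 17 per group is reproduced at this SD.
- SD 0.53, n = 17: 0.5 / (0.53 × √(2/17)) = 2.75; power 76.0%.
- SD 0.53, n = 20 (all 40 analysed): 0.5 / (0.53 × √(2/20)) = 2.98; power 82.8%.

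**Adjusted power, one covariate.** With N patients in total, the residual SD is SD × √(1 − R²) and the df are N − 3. The variance of the arm difference is multiplied by 1/(1 − r), where r ~ Beta(1/2, (N − 2)/2) represents chance imbalance in the covariate. Power is averaged over r. At SD 0.53 the residual SD is 0.530, 0.503, 0.474 and 0.443 for R² = 0, 0.1, 0.2 and 0.3.

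| Setting | Unadjusted | R² = 0 | 0.1 | 0.2 | 0.3 |
|---|---|---|---|---|---|
| 17 per arm, SD 0.53 | 76.0% | 74.6% | 78.9% | 83.4% | 87.9% |
| 17 per arm, SD 0.50 | 80.7% | 79.4% | 83.4% | 87.4% | 91.3% |
| 20 per arm, SD 0.53 | 82.8% | 81.8% | 85.6% | 89.3% | 92.8% |

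Simulation of the first row (40,000 trials per setting) gave 74.2%, 78.9%, 83.3% and 88.2%. A separate simulation under no difference kept the ANCOVA type I error between 4.8% and 5.2%.

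For the first row, break-even is at R² of about 0.034 (correlation √0.034 ≈ 0.18), and 80% power needs R² of about 0.12 (correlation about 0.35). If thickness is not prognostic, the loss is 76.0 − 74.6 = 1.4 points. A second covariate costs more: 73.1% at R² = 0, a loss of about 3 points, which is hard to justify at 17 per arm.

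**Range restriction.** Eligibility limits the crest position and any fenestration, which may narrow the spread of thickness. If it halved the variance of thickness (assumed), R² would become 0.5R² / (0.5R² + 1 − R²). Values of 0.1, 0.2 and 0.3 would then fall to about 0.05, 0.11 and 0.18. With total SD held at 0.53, the gain over the unadjusted test is about 1, 3 and 6 points. With residual SD held fixed instead, the power levels are higher but the gains are similar (about 1, 3 and 5 points).

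**Why item 2c and no other site measurement.** The reference notch is cut 2 mm from the margin, so the starting notch distance varies little by design. The horizontal and vertical defect dimensions are measured from the implant shoulder, so they come after randomisation. Item 2c is midbuccal only, so it bears on the midbuccal margin and not on the two papillary sites.

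**Where item 2c is read.** It is taken 6 mm apical to the gingival margin, and the crest must lie within 4 mm of that margin. The reading is therefore at least 6 − 4 = 2 mm below the crest, away from the tissue whose recession is measured.

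**The case against.** The strongest reply is that nothing is broken. Under randomisation the unadjusted test is valid, and choosing between valid analyses is partly a matter of preference. That stands, and it is why this point is optional.

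The reply also holds that the benefit rests on an R² the documents do not give, for a reading taken below the crest in a selected population. That stands too: at R² = 0.1 the gain is 2.9 points (78.9 − 76.0), or about 1 point if the spread of thickness is halved. With all 40 patients analysed, the unadjusted test already has 82.8%.

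Third, "measured at implant placement only" may simply name the visit, as the other items on the list do. That is a natural reading. What remains is narrower: the order of the reading relative to randomisation and flap elevation is not written down.

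Three stronger inferences are tempting and are not supported.

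- A reader might infer that the planned test is wrong or the trial underpowered. The planning SD is not stated, and 17 per group gives 80.7% at SD 0.50; the 76.0% depends on borrowing the background SD.
- A reader might infer that thickness is read after allocation. The text leaves the order open; it does not say so.
- A reader might infer that adjustment will clearly raise power. The rationale names risk indicators but gives no correlation.

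**Conclusion.** A cheap, optional improvement, not an error in the plan. The stated analysis of continuous outcomes is unadjusted, although a plausible prognostic reading is already collected at the midbuccal site. The trade is lopsided: at 17 per arm and SD 0.53, about 1.4 power points are lost if thickness is not prognostic, against about 3, 7 and 12 gained at R² of 0.1, 0.2 and 0.3. These figures assume two-sided alpha 0.05, the background SD, a normal covariate and an R² the documents do not supply. The realised gain may be at the low end, or absent, given where the reading is taken and the eligibility limits. The sample size need not change. Item 2c should be clarified before any use of the reading as a baseline value, whether or not the adjustment is adopted.

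**What to change.** 1. In Study Procedures and Research Procedures, state that item 2c is recorded after extraction and before randomisation and any flap elevation, alongside the crest check that Inclusion Criteria already places there. State whether it is one combined reading or separate soft-tissue and plate readings.
2. Prespecify an ANCOVA of the midbuccal margin change at 12-18 months on arm plus one thickness covariate named in advance, reporting the adjusted difference with its 95% CI.
3. Name a rank-based ANCOVA as the adjusted fallback for non-normal data, and say in advance which analysis is primary.
4. Keep the unadjusted t-test and Wilcoxon test as sensitivity analyses.

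The cost is analysis wording and one procedure line, which may change the order of measurements on the day of surgery. No new patients, visits or data are needed for a single covariate.

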### **Study Procedures**

After informed consent is obtained, and initial periodontal therapy, whenever indicated, the scheduled extraction will be carried out without flap elevation, and the socket will be debrided meticulously. After verification that the local anatomical inclusion criteria are met, patients will be randomized to one of two treatment groups, a test (flapless group) and a control group (flap group). In the test group, the implant will be placed according to standard protocol at a position engaging the palatal wall without elevation of a mucoperiosteal flap. In the control group, intrasulcular incisions will be carried out from one tooth distal to one tooth mesial to the extraction site and full thickness flaps will be elevated with periosteal elevator, including the papillae. The implant will be placed according to standard protocol at a position engaging the palatal wall, and the flaps will be sutured using a combination of interrupted and mattress sutures.

In both groups, temporary restorations will be delivered immediately after implant placement provided that the implant shows primary stability and has engaged in the bone with an insertion torque of 25Ncm or more (Norton, 2004). In case of a lower insertion torque, the protocol will be abandoned, a cover screw will be placed, and a two stage implant protocol will be followed. All patients will be advised to receive a permanent restoration 6 months after surgery, if the implant is deemed to be successful (Misch et al., 2008).

All patients will receive antibiotics 1 hour prior to surgery (Amoxicillin 1g; in allergic patients Clindamycin 300mg) and will continue with Amoxicillin 500mg (Clindamycin 150 mg) tid for seven days following surgery. All patients will be seen 1 week following surgery (suture removal visit, if applicable), review of OH; at two weeks following surgery, follow up of healing and OH; at 4 weeks, 6 weeks and 8 weeks (prophylaxis and measurements); at 3 months (prophylaxis and measurements); at 6 months (prophylaxis, measurements; removal of temporary restorations and impressions for permanent prosthesis, which will be delivered subsequently, can be done by restorative dentist or student at this visit or later) and at 12-18 months (prophylaxis, measurements).

